5. STUDY DESIGN

5.1. Overview of Study Design

This is a phase I/II study in which patients will be enrolled in a standard 3+3 design. Once the maximum tolerated dose (MTD) is determined amongst patients with relapsed or refractory grade 1-3a follicular lymphoma, there will be a 17-patient phase II study.

5.2. Treatment Plan

5.2.1 Phase I Study Treatment Plan

Patients will be treated with combination therapy of ibrutinib and venetoclax according to their assigned dose level cohort. Dose escalation is described in Table 2 and the paragraph below.

Each cycle is 28-days. Patients will be monitored for dose limiting toxicity (DLT) weekly during Cycle 1. Patients will receive the combination until progression or unacceptable toxicity. Patients will be followed during therapy through progression until next line of therapy. Questions regarding treatment should be directed to the Study Chair.

Table 2: Dose Level Cohorts

Dose Levels		
Dose Level	Ibrutinib	Venetoclax
0	420 mg	400 mg
1	560 mg	400 mg
2	560 mg	600 mg

*Dose Level 0 is the starting level dose

The MTD finding procedure starts at DL0. Three patients will initially be entered at this dose level.

- If 0/3 DLT is observed, dose escalation will continue to the next upper dose level.
- If $\geq 2/3$ DLTs are observed, then the dose finding procedure will be terminated.
- If 1/3 DLT is observed, then 3 additional patients will be enrolled in the same dose level. If no DLT is observed from the additional 3 patients, then dose escalation will continue to the next upper dose level. If any DLT is observed from the 3 additional patients, then the

previously lower dose will be chosen as the MTD and the dose finding procedure will be terminated.

Dose escalation will be continued as per Table 2 until a dose with no more than 1/6 DLTs is found and is chosen as the MTD. Once the MTD is determined, there will be a 17-patient phase II study at this dose level.

The original design of this study included a Dose Level 3 of Ibrutinib 560 mg and Venetoclax 800 mg. After examining the pharmacokinetic data at Dose Level 2, which showed a significantly increased systemic plasma exposure to ibrutinib, it was determined not to proceed with Dose Level 3. One patient had initiated therapy at Dose Level 3 before the decision was made for closure.

5.2.2 Phase II Study Treatment Plan

Patients will be enrolled at the recommended phase II dose. Duration of therapy will depend on depth of response. Patients who achieve a complete remission may discontinue therapy after 24 cycles. These patients must undergo a PET-CT during Cycle 24 to confirm they are still in a complete remission prior to discontinuation. Patients who achieve a partial response will continue therapy until progression or unacceptable toxicity. Patients will be followed throughout the duration of therapy through progression until next line of therapy. Patients who achieve a complete remission and discontinue therapy after 24 cycles will be monitored closely per Table 1 and may be reinitiated on treatment within one year of discontinuation for either progression of disease or at the discretion of the treating physician.

Ibrutinib (capsules) and venetoclax (tablets) should be administered orally once daily at the same time. The capsules and tablets are to be taken at the same time each day with 8 ounces (approximately 240 mL) of water. The capsules and tablets should be swallowed intact and subjects should not attempt to open capsules or tablets or dissolve them in water. The first dose will be delivered in the clinic on Day 1, after which subsequent dosing is typically on an outpatient basis. All subjects must be trained to self-administer therapy orally 30 minutes after the completion of breakfast or the subject's first meal of the day. If a dose is not taken at the scheduled time, it can be taken as soon as possible on the same day with a return to the normal schedule the following day. Subject should not take extra capsules or tablets to make up the missed dose.

At study entry, patients will receive a Medication Calendar, and will be instructed on how to use the Medication Calendar. Study drugs will be dispensed to subjects in bottles at each visit. At monthly visits, the patient will bring the Medication Calendar to the clinic. All bottles of study medication (full, partial, and empty) should be brought to the clinic to compare with the Medication Calendar. The Medication Calendar for the previous month will be reviewed, and new Medication Calendar will be given to the patient (APPENDIX V). Unused study drugs

dispensed during previous visits must be returned to the site. Returned capsules and tablets must not be re-dispensed to anyone.

5.3. Prophylaxis and Management of Tumor Lysis Syndrome

5.3.1. Prophylaxis for Tumor Lysis Syndrome

TLS is a risk for patients with NHL who are treated with high cell-killing agents. Risk is highest for those with bulky disease, elevated pretreatment lactate dehydrogenase (LDH) levels, elevated leukocyte count, and dehydration. Patients with bulky disease, defined as any lymph node ≥ 8 cm on the screening CT scan, and/or lymphocytosis due to circulating lymphoma cells, are considered at higher risk of TLS and must be hospitalized for more intensive monitoring during the initial dose of study drugs. Patients who do not present with bulky disease are not considered at higher risk for TLS and do not require hospitalization, but may be hospitalized per discussion with the investigator and Medical Monitor.

All patients must receive prophylaxis for TLS prior to the initiation of the first dose of the study drugs. Prophylaxis will include the following:

- Appropriate hydration, consisting of a fluid intake of approximately 2-3L/day starting 24-48 hours days prior to start of the study drugs and continued for at least 24 hours after the first does (for patients for whom volume overload is considered a significant risk, hospitalization should be considered).
- Administration of an agent to reduce uric acid, such as allopurinol 300 mg/day, orally beginning 72 hours prior to the first study drugs dose. Rasburicase IV should be administered (unless medically contraindicated) for those patients with elevated uric acid levels prior to treatment which is, defined as a value above the local laboratory ULN or 476 $\mu\text{mol/L}$. Agents should be given until normalization of serum uric acid and other laboratory evidence of TLS (e.g. elevated serum LDH levels).
- Laboratory results should be reviewed, and electrolyte values should not demonstrate any clinically significant abnormalities prior to the first dose of study drugs or the patient should receive additional prophylactic treatment and hydration prior to the initiation of dosing.
- Patients at higher risk of TLS will be hospitalized for initial study drugs dose.
- For patients at particularly high risk for TLS, as judged by the investigator, consideration may be given to starting at a lower dose of study drugs and increasing study drugs dose in a stepwise fashion in discussion with the Medical Monitor.

On the day of initial visit with administration of study drugs, serial vital sign assessments will be performed, and serum chemistry and hematology samples will be drawn prior to the dose of

study drugs and at 8 and 24 hours following the dose. The serum chemistry and hematology samples will be immediately sent to the laboratory and the investigator or designee must promptly review the results. Laboratory results from pre-dose samples must be reviewed prior to study drugs administration unless laboratory results from within the prior 24 hours have already been reviewed and do not require intervention. Laboratory values obtained prior to the dose of study drugs are to be used to determine whether a patient developed a change related to TLS. Laboratory results from the 24-hour post-dose assessments must be reviewed prior to receiving the dose of study drugs for that day.

Patients who develop electrolyte changes suggestive of TLS should undergo aggressive management and further monitoring per Appendix VII. Definitions of Laboratory and Clinical Evidence of Tumor Lysis Syndrome are listed in Appendix VIII. In addition:

- The next day's dose of venetoclax should be held. If electrolyte changes are resolved within 24-48 hours of the last dose, venetoclax should be resumed at the same dose.
- For any electrolyte changes requiring more than 48 hours to resolve, venetoclax should be resumed at a dose of 100 mg less than the last dose.
- For any events of clinical TLS, venetoclax should be resumed at a dose of 100 mg less than the last dose following resolution of the TLS.

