1.8.1. Risks with Venetoclax

1.8.1.1. Tumor Lysis Syndrome

As a result of on-target effects, the potential for tumor lysis syndrome (TLS) was identified early in the program.

Overall, the clinical data strongly support that the risk of TLS with venetoclax in CLL/SLL subjects is characterized as highest when initiating venetoclax dosing, especially with a higher initial dose of venetoclax, as well as being greater in subjects with a large tumor burden. The available data suggest that in non-CLL subjects the risk of TLS is low. It is being closely monitored among subjects with AML, NHL and MM. There have two cases of TLS in NHL, one patient with DLBCL and one patient with mantle cell lymphoma.

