5.3.2. Hospitalization

Patients at higher risk for TLS (any lymph node \geq 8 cm and/or circulating lymphoma cells) must be hospitalized for the initial dose of study drugs. Hospitalization should also be considered for patients with creatinine clearance $<$ 80 mL/min, in discussion with the study chair, [name]. Hospitalization will begin the evening prior to the first dose of study drugs and continue for 24 hours after. Upon admission, serum chemistry and hematology laboratory samples should be drawn, and IV hydration should be started with a target of 150-200 cc/hr or as clinically appropriate. Laboratory results should be reviewed, and electrolyte values should not demonstrate clinically significant abnormalities prior to the first dose of study drugs, or the patient should receive additional prophylactic treatment and hydration prior to the initiation of dosing. A nephrologist (or acute dialysis service) must be consulted/contracted on hospital admission (per institutional standards) to ensure emergency dialysis is available and the appropriate staff is aware and prepared to handle any necessary intervention for TLS. Telemetry should also be considered.

Serial vital sign assessments will be performed, and TLS laboratory samples will be drawn prior to the first dose of study drugs at 8, 12, and 24 hours post-dose, additionally, hematology samples will be drawn at 8 and 24 hours post-dose. These samples are to be immediately sent to the laboratory and the investigator or designee must promptly review the results. Laboratory values obtained prior to the dose of study drugs are to be used to determine whether a patient

developed a change related to TLS. Patients are still considered eligible to initiate therapy on Cycle 1 Day 1 if their hematologic parameters have dropped below eligibility requirements due to aggressive intravenous hydration. Laboratory results from the 24-hour post-dose sample must be reviewed prior to receiving the dose of study drugs for that day. Patients who develop electrolyte changes suggestive of TLS should undergo aggressive management and further monitoring per Appendix VII. Reintroduction of venetoclax in these patients should be performed as described in Section 5.3.1.

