APPENDIX VIII RECOMMENDATIONS FOR INITIAL MANAGEMENT OF ELECTROLYTE

ABNORMALITIES AND PREVENTION OF TUMOR LYSIS SYNDROME

- Within the first 24 hours after either the first dose or dose increase, if any laboratory criteria below are met, the patient should be hospitalized for monitoring and the investigator notified. No additional study drugs doses should be administered until resolution. A rapidly rising serum potassium level is a medical emergency.
- Nephrology (or acute dialysis service) must be consulted/contacted on admission (per institutional standards to ensure emergency dialysis is available).
- Intravenous (IV) fluids (e.g. D5 ½ normal saline) should be initiated at a rate of at least 1 mL/kg/h rounded to the nearest 10 mL (target 150 to 200 mL/h; not < 50 mL/h). Modification of fluid rate should also be considered for individuals with specific medical needs.
- Monitor for symptoms or signs of tumor lysis syndrome (TLS; e.g. fever, chills, tachycardia, nausea, vomiting, diarrhea, diaphoresis, hypotension, muscle aches, weakness, paresthesias, mental status changes, confusion, and seizures). If any clinical features are observed, recheck potassium, phosphorous, uric acid, calcium and creatinine within 1 hour.
- Vital signs should be taken at time of all blood draws or any intervention
- The management recommendations below focus on the minimum initial response required. If a diagnosis of TLS is established, ongoing intensive monitoring and multi-disciplinary management will be as per institutional protocols.

Abnormality	Management Recommendations
Hyperkalemia (including rapidly rising potassium)	
Potassium \geq 0.5 mmol/L increase from prior value (even if potassium within normal limits [WNL])	
Recheck potassium, phosphorus, uric acid, calcium and creatinine in 1 hour STAT. If further \geq 0.2 mmol/L increase in potassium, but still < upper limit of normal (ULN), manage as per potassium \geq ULN. Otherwise recheck in 1 hour.
 
Resume per protocol testing if change in potassium is < 0.2 mmol/L, and potassium < ULN, and no other evidence of tumor lysis.
 
At the discretion of the investigator, may recheck prior to hospitalization. If stable or decreased, and still WNL, hospitalization is at the discretion of the investigator. Potassium, phosphorus, uric acid, calcium and creatinine must be rechecked within 24 hours.

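### Sections 5.3.1 and 5.3.2 give conflicting first-dose admission rules for patients with circulating lymphoma cells but no node of 8 cm or more

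*Combined protocol and SAP*

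**What the plan says.** Section 5.3.1 defines bulky disease as any node of at least 8 cm on the screening CT. Patients with that finding "and/or lymphocytosis due to circulating lymphoma cells, are considered at higher risk of TLS and must be hospitalized for more intensive monitoring" when they take the first dose. The sentence that follows reads: "Patients who do not present with bulky disease are not considered at higher risk for TLS and do not require hospitalization, but may be hospitalized", subject to discussion with the investigator and Medical Monitor. A later bullet in 5.3.1 repeats that higher-risk patients are admitted, without restating who they are.

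Section 5.3.2 says that higher-risk patients, identified as those with any node of at least 8 cm "and/or circulating lymphoma cells) must be hospitalized for the initial dose of study drugs".

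The monitoring differs by setting. Section 5.3.1 has chemistry and hematology drawn before the dose of "study drugs and at 8 and 24 hours following the dose". For admitted patients, 5.3.2 says "TLS laboratory samples will be drawn prior to the first dose of study drugs at 8, 12, and 24 hours post-dose", and "Hospitalization will begin the evening prior to the first dose of study drugs and continue for 24 hours after". Appendix VIII adds that in the first 24 hours after the first dose or a dose increase, "if any laboratory criteria below are met, the patient should be hospitalized for monitoring and the investigator notified". On background risk, Section 1.8.1.1 states: "The available data suggest that in non-CLL subjects the risk of TLS is low".

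**The concern.** There are two separate wording faults.

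- The exemption in 5.3.1 is meant to be the complement of the rule just before it, but it mentions only bulky disease. Taken literally, it releases non-bulky patients with lymphocytosis from circulating lymphoma cells, whom the preceding sentence and 5.3.2 both require to be admitted.
- The blood criterion itself differs. Section 5.3.1 needs lymphocytosis; 5.3.2 needs only the presence of circulating lymphoma cells.

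This is a mandatory safety rule for the first dose of both drugs. Venetoclax starts at 400 or 600 mg (Table 2), and a lower start with stepwise increase is only an option for patients judged at particularly high risk. Three centers take part. A center that treats such a patient as an outpatient complies with 5.3.1 and breaches 5.3.2, so neither the center nor a monitor can say whether the protocol was followed.

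**Working it through.** No sample size, power or error rate is involved. The check is to cross the node criterion with the blood finding and read each case against the three sentences.

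| Case | 5.3.1 mandatory sentence | 5.3.1 exemption | 5.3.2 mandatory sentence | Result |
|---|---|---|---|---|
| (a) Node ≥ 8 cm, any blood finding | Admit | Does not apply | Admit | Consistent |
| (b) No such node, no circulating cells | Does not apply | Not required | Does not apply | Consistent |
| (c) No such node, circulating cells, normal lymphocyte count | Does not apply | Not required | Admit | 5.3.1 and 5.3.2 conflict |
| (d) No such node, lymphocytosis from circulating cells | Admit | Not required (literal reading) | Admit | 5.3.1 conflicts with itself |

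The punctuation in 5.3.1 would allow lymphocytosis to be read as part of the definition of bulky disease. On that reading case (d) becomes consistent. Case (c) does not, because those patients have no lymphocytosis.

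The difference in scheduled post-dose TLS chemistry follows from the two sampling schedules:

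- Not admitted (5.3.1): 8 h and 24 h, so 2 draws. Longest gap = 24 − 8 = 16 h.
- Admitted (5.3.2): 8 h, 12 h and 24 h, so 3 draws. Longest gap = 24 − 12 = 12 h.

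Hematology is at 8 h and 24 h in both settings, and pre-dose samples are taken in both. Admission also brings entry the evening before, labs on arrival, IV hydration at a target of 150–200 cc/hr, and contact with nephrology or the dialysis service in advance.

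**The case against.** The best defense combines two charitable readings. In the first, bulky disease in the exemption is shorthand for the whole higher-risk definition in the sentence before, so case (d) was never in doubt; three statements already require admission there. In the second, the parenthesis in 5.3.2 merely abbreviates the 5.3.1 definition, so case (c) vanishes too. Both readings are possible, but neither is compelled by the text, and both are needed at once to make the sections agree. The first alone leaves case (c); the second alone leaves case (d).

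The points on consequence are stronger, and they stand:

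- The group is small as far as one can tell. The schedule of events has a CBC with differential but no blood flow cytometry, so some of these patients would not be identified at all. The two NHL cases of TLS cited in 1.8.1.1 were in diffuse large B-cell and mantle cell lymphoma.
- Every patient has hydration, a uric-acid-lowering agent, serial vital signs and pre-dose, 8 h and 24 h labs, with the 24 h result reviewed before the next dose. Appendix VIII also asks for chemistry within 1 hour if symptoms appear, so detection does not rest on the scheduled draws alone.
- Section 5.3.1 permits admission after discussion.

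It is also fair to say that choosing the 5.3.2 criterion is a decision, not a pure correction. Section 5.3.1 lists an elevated leukocyte count among the risk factors, which could mean that lymphocytosis was intended.

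**Conclusion.** The inconsistency is real and should be corrected. On any reading of bulky disease, unless 5.3.2 is also taken as an abbreviation of 5.3.1, patients with circulating lymphoma cells, a normal lymphocyte count and no node of 8 cm or more fall under a mandatory rule in one section and a discretionary one in the other. On the literal reading, 5.3.1 also contradicts itself for non-bulky patients with lymphocytosis.

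The consequence is limited to first-dose safety conduct in a narrow group: one 12-hour TLS sample and the other elements of admission. The documents do not give the group's share; that it is small is a judgment, resting on the low non-CLL risk stated in the protocol and on the absence of flow cytometry. No endpoint, DLT definition, sample size or error rate changes.

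**What to change.** Rewrite two sentences in 5.3.1 and leave 5.3.2 as it is:

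- Mandatory rule: a patient with any node of 8 cm or more on the screening CT, with circulating lymphoma cells, or with both, is at higher risk of TLS and must be admitted for the first dose.
- Exemption: only a patient with neither feature is not at higher risk; admission is then optional, after discussion with the investigator and Medical Monitor.

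This keeps the broader of the two requirements already in the protocol. If the sponsor did intend lymphocytosis to be necessary, that condition should go into both sections instead. The exemption needs repair either way, because it must name the blood criterion.

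The cost is the two sentences and possibly a few more short admissions, each from the evening before the first dose until 24 hours after it. No CRF field or analysis changes.

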APPENDIX VI DRUGS TO BE AVOIDED OR USED WITH CAUTION**PROHIBITED MEDICATIONS**

Warfarin (Coumadin)
 Biologic agents
 Anticancer therapy
 Other investigational agents
 Steroid therapy for anti-neoplastic intent

CYP3A Strong Inhibitors

Atazanavir
 Clarithromycin
 Itraconazole
 Fluvoxamine
 Nefazodone
 Nelfinavir
 Ritonavir
 Saquinavir
 Telithromycin
 Voriconazole
 Ketoconazole
 Boceprevir
 Cobicistat
 Conivaptan

Indinavir
 Lopinavir
 Mibefradil
 Posaconazole
 Telaprevir
 Troleandomycin

CYP3A Moderate Inhibitors

Fluconazole
 Aprepitant
 Erythromycin
 Diltiazem
 Verapamil
 Amprenavir
 Atazanavir
 Ciprofloxacin
 Crizotinib
 Darunavir
 Dronedaron
 Fosamprenavir
 Imatinib
 Grapefruit juice

Seville orange juice

CYP3A Strong Inducers

Avasimibe
 Carbamazepine
 Mitotane
 Modafinil
 Phenobarbital
 Phenytoin
 Rifabutin
 Rifampin
 St. John's Wort

CYP3A Moderate Inducers

Bosentan
 Efavirenz
 Etravirine
 Modafinil
 Nafcillin
 Oxcarbazepine
 Troglitazone

MEDICATIONS TO USE WITH CAUTION**CYP3A Weak Inducers**

Armodafinil
 Clobazam
 Pioglitazone
 Glucocorticoids such as prednisone
 Rufinamide
 Nevirapine
 Pioglitazone
 Vemurafenib

CYP3A Weak inhibitors

Alprazolam
 Amlodipine
 Atorvastatin
 Cimetidine
 Ranitidine
 Amiodarone
 Bicalutamide
 Cilostazol
 Cyclosporine
 Fluvoxamine
 Fluoxetine
 Ginkgo

Goldenseal
 Isoniazid
 Nilotinib
 Oral contraceptives
 Pazopanib
 Ranitidine
 Ranolazine
 Suboxone
 Tipranavir
 Ticagrelor
 Zileuton

Note that this is not an exhaustive list. Further information can be found at the following websites:

<http://medicine.iupui.edu/clinpharm/ddis/main-table/>

and

<http://www.fda.gov/Drugs/DevelopmentApprovalProcess/DevelopmentResources/DrugInteractionsLabeling/ucm080499.htm>.

APPENDIX VII LUGANO REVISED RESPONSE CRITERIA FOR NON-HODGKIN LYMPHOMA 32

Site	PET-CT- Based Response	CT-Based Response
Complete Response	Complete metabolic response	Complete radiologic response (all of the following):
Lymph nodes & extralymphatic sites	Score 1, 2, or 3 with or without a residual mass on 5-point scale	Target nodes/nodal masses must regress \leq 1.5cm in longest transverse diameter of a lesion (LDi); no extralymphatic sites of disease
Non-measured lesion	NA	Absent
Organ enlargement	NA	Regress to normal
New Lesions	None	None
Bone Marrow	No evidence of FDG-avid disease in marrow	Normal by morphology; if indeterminate, and flow cytometry IHC negative
Partial Response	Partial metabolic response	Partial remission (all of the following):

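### Sections 5.3.1 and 5.3.2 cite the wrong appendices for tumor lysis syndrome (TLS), and the one hold instruction in 5.3.1 omits ibrutinib, which Appendix VIII also holds in the 24 hours after a first dose or dose increase

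*Combined protocol and SAP*

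**What the plan says.** Section 5.3.1 tells sites that patients with electrolyte changes pointing to TLS need aggressive management and "further monitoring per Appendix VII. Definitions of Laboratory and Clinical Evidence of Tumor Lysis Syndrome are listed in Appendix VIII". Section 5.3.2, for hospitalized patients, also asks for "further monitoring per Appendix VII".

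The appendix headings read differently: "APPENDIX VII LUGANO REVISED RESPONSE CRITERIA FOR NON-HODGKIN LYMPHOMA" and "APPENDIX VIII RECOMMENDATIONS FOR INITIAL MANAGEMENT OF ELECTROLYTE". The laboratory and clinical definitions of TLS are in Appendix IX. The contents list gives the same numbering.

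On holding and restarting, Section 5.3.1 adds three bullets. The first says that the next day's "dose of venetoclax should be held" and allows restart at the same dose if the changes resolve within 24 to 48 hours. The second and third lower the venetoclax restart dose by 100 mg, after slower resolution or after clinical TLS. Section 5.3.2 has no hold rule of its own. It says: "Reintroduction of venetoclax in these patients should be performed as described in Section 5.3.1".

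Appendix VIII sets a different scope: "Within the first 24 hours after either the first dose or dose increase, if any laboratory criteria below are met", the patient should be hospitalized, the investigator notified, and further doses of the study drugs, in the plural, withheld until resolution. The dose-increase trigger can apply here, because for patients at particularly high risk Section 5.3.1 permits "starting at a lower dose of study drugs and increasing study drugs dose in a stepwise fashion".

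**The concern.** The miscited appendices carry content that Section 5.3 does not repeat. The post-dose laboratory thresholds, the rapid rechecks and the hold on both drugs are in Appendix VIII. The definition of clinical TLS, on which the third 5.3.1 bullet bases its 100 mg venetoclax reduction, is in Appendix IX. A site that follows the management pointer arrives at imaging criteria.

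A site that then works from the body text alone sees a hold on venetoclax and nothing about ibrutinib. The two drugs are taken together once daily (Section 5.2.2), so for a patient with an early laboratory signal the question arises at the next scheduled dose. Ibrutinib is not irrelevant to TLS: Section 1.5.1.8 lists TLS among its risks, and Appendix I records it as an expected serious reaction in 10 of 3,597 subjects (0.3%).

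**Working it through.** No arithmetic applies and there is no planned figure to reproduce. The check compares each pointer with the appendix it should reach, and then each hold or restart statement with Appendix VIII.

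**Pointers**

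| Place | Subject | Cited | Appendix cited contains | Correct |
|---|---|---|---|---|
| 5.3.1 | TLS management | VII | Lugano criteria | VIII |
| 5.3.2 | TLS management | VII | Lugano criteria | VIII |
| 5.3.1 | TLS definitions | VIII | TLS management | IX |

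All three are wrong, each by one.

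The definitions pointer is not harmless. Appendix VIII acts on single abnormalities, for example phosphorus of at least 5.0 mg/dL with a rise of at least 0.5 mg/dL. Appendix IX requires two or more metabolic abnormalities in the same 24 hours for laboratory TLS, and additional clinical features for clinical TLS. A site that took the Appendix VIII thresholds as the definition would classify patients differently.

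**Hold and restart statements**

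1. 5.3.1, first bullet: hold venetoclax, with a same-dose restart if resolved in 24 to 48 hours. Its first sentence is the only hold instruction among these statements.
2. 5.3.1, second bullet: venetoclax restart dose after slower resolution.
3. 5.3.1, third bullet: venetoclax restart dose after clinical TLS.
4. 5.3.2: venetoclax reintroduction, by reference to 5.3.1.

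Appendix VIII gives no restart dose for either drug, so items 2 to 4 cannot conflict with its hold. The discrepancy is confined to the hold sentence in item 1, and only where the Appendix VIII rule applies: a listed criterion met within 24 hours of the first dose or a dose increase. None of the four statements says what happens to ibrutinib, and Section 5.3 gives no ibrutinib restart dose.

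**Does another rule close the gap?** Section 6.2 and Table 4 withhold both study drugs for non-hematologic toxicity of Grade 3 or higher. That covers a TLS event of that grade; Section 1.7.2 describes laboratory TLS as Grade 3. Appendix VIII starts lower: its first potassium row is triggered by a rise of 0.5 mmol/L even when the value is still normal. Section 5.3 does not cite Table 4, and Table 4 would not reach such changes.

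**The case against.** The strongest reply is that the texts are compatible. The 5.3.1 bullets are introduced as additions to the appendix guidance, and no sentence tells a site to continue ibrutinib. A reader with both texts can hold the study drugs under Appendix VIII and restart venetoclax at the 5.3.1 dose. This stands. A reader might infer that the protocol contradicts itself or directs that ibrutinib continue; the documents do not support that. Nor do they support reading Appendix VIII as an unrestricted hold on both drugs, or treating all four venetoclax-only statements as hold errors.

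Other safeguards also count. The contents list titles the appendices correctly. The mistaken definitions pointer happens to land on the management appendix. The 24-hour results must be reviewed before that day's study drugs. Table 4 covers higher-grade events. Section 1.8.1.1 describes TLS risk as low outside CLL.

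Finally, the numbering slip is not peculiar to TLS: FLIPI and ECOG in Section 3.1, Lugano in Section 12.2 and ibrutinib sample collection in Section 5.4.2 are also cited one number low. This suggests an editorial cause.

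These points reduce the risk but do not remove it. The reconciled reading depends on finding the appendix that the text miscites. Section 5.3 elsewhere writes study drugs when it means both agents, so a site could reasonably take a bullet naming one drug as deliberate.

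**Conclusion.** The pointer error is certain: three of three TLS pointers in 5.3.1 and 5.3.2 are wrong. The hold problem is narrower. One instruction is incomplete for ibrutinib within the Appendix VIII window, and the practical exposure is electrolyte changes below Grade 3, where Table 4 gives no cover. It should be corrected because it sits in operative safety text, but the safeguards above do not justify a higher rating. Sample size and error rates are unaffected.

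The conclusion assumes that study drugs in Appendix VIII means both agents, as it does elsewhere in Section 5.3, and that the Appendix VIII rule is the intended one. If the sponsor meant a venetoclax-only hold, Appendix VIII is the text to change; the two passages would still need to be aligned.

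**What to change.** - Change the management pointers in Sections 5.3.1 and 5.3.2 from Appendix VII to Appendix VIII, and the definitions pointer in 5.3.1 from Appendix VIII to Appendix IX.
- Amend the first 5.3.1 bullet to say that when an Appendix VIII laboratory criterion is met within 24 hours of the first dose or a dose increase, both ibrutinib and venetoclax are held until resolution. Keep that window in the bullet: without it the ibrutinib hold would extend beyond what Appendix VIII provides, which is a clinical decision for the sponsor.
- Leave the existing venetoclax restart doses unchanged, and add a sentence giving the ibrutinib restart dose, which the sponsor must specify.

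The cost is protocol wording only: three cross-references, one bullet and one added sentence. Design, sample size and data collection do not change.
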